Précis: This is a phase 2, single center, two-arm double-masked, randomized investigation and modulation of the μ -opioid mechanisms in TMD (in vivo). We will enroll 60 patients with chronic TMD (30 for the active M1 HD-tDCS group and 30 for the sham group). Each participant will undergo the sequence of events and evaluations laid out in the Schematic of Study Design (pages 14-15), which will take approximately 3 months (up to 10 weeks for healthy volunteers [HV]). In addition, we will recruit 20 (or more) age- and gender-matched HV. We will use the PET/MRI data from up to 10 healthy controls who were recruited and scanned during the NIDCR-NIHR56 DE022637 project, for a total of 30 HV. These 30 healthy control volunteers will be compared to TMD patients at baseline; however, they will not be part of the clinical trial. Completion of full protocol enrollment and participation is expected to take approximately 5 years. Data will be collected on paper or electronic CRFs, on mobile devices, or electronically on local systems (PET, MRI, QST), then transferred via HIPAA-compliant methods by the Michigan Medicine system for analysis by study staff.

Objectives: Primary Objective: The primary effectiveness objective is to investigate whether 10 daily sessions of primary motor cortex (M1) HD-tDCS will result in a significant reduction in clinical pain intensity at rest in chronic TMD subjects 4 weeks after completion of HD-tDCS sessions, as measured by a visual analog scale (VAS) pain score.

The secondary objectives are as follows:

- To investigate whether 10 daily sessions of M1 HD-tDCS will result in significant reductions in clinical pain intensity (at rest) and experimental (sustained masseteric pain stress challenge) measures in chronic TMD subjects at 1 week after completion of HD-tDCS sessions, as measured by VAS pain score assessments, obtained during the baseline PET (#1) session and follow-up PET (#2) session.
- To investigate whether 10 daily sessions of M1 HD-tDCS will result in significant short-term and/or long-term changes

in clinical pain intensity and area measures in chronic TMD subjects treated with HD-tDCS compared to those who receive sham treatment, as measured by GeoPain measures.

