provided by the device, ≤ 2 mA for subjects in the active arm of this study, is equally distributed between the 2 anodes (1 mA per anode). The operation of the electrodes is controlled through a unit on which the current level and treatment time are set by the investigator's unblinded designee before each treatment session. The unit also has a "Relax" feature that, when switched on by the designee, immediately ramps down the current by 0.2 to 0.5 mA for a few seconds if a subject communicates they are experiencing discomfort. This unit has been inspected by the University of Michigan (UM) biomedical engineering unit and found to be in compliance with all regulations. The electrodes are connected to the unit by 4 identical smooth, rounded, red cables measuring 39.5 cm in length. The control unit and cables are shown in Figure 3b.

As shown in Figure 3a, the upper anode will be placed on C3-4, the lower anode on C5-6, and the upper and lower cathodes will be placed anteriorly on FC3-4 and FC5-6, respectively, using the standard International Electroencephalography (EEG) 10-20 system¹². The vertex will be found by measuring the midpoint between nasion and inion and the midpoint between the pre-auricular areas; then, the midpoint from the vertex to the pre-auricular point on the side contralateral to the patient's worst pain will be marked so that stimulation can be applied to the same spot each day. A perforated fabric cap with a chinstrap will then be placed on the head to secure plastic casings in the desired position of each electrode (Figure 3a), and approximately 3 mL of Lectron II Conductive Gel (K933804) will be injected into the casings. The electrodes will be placed in the gel with the rough surface directed toward the skin and held in place with plastic caps¹³. For subjects in the active HD-tDCS group, ≤ 2 mA total current stimulation will be applied for 20 min. For subjects receiving the sham-controlled tDCS sessions, current will be applied for 30 seconds at the beginning and at the end of the treatment sessions, as sensations arising from tDCS treatment occur mostly at the beginning and end of application. The control panel will not be visible to subjects or blinded investigators during treatment. The unit will be continually monitored by the designee throughout each treatment session.

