5.4 Treatment Assignment Procedures

5.4.1 *Randomization Procedures*

Participants initially will be screened by phone. After clinical exam and diagnosis of the DC/TMD Axis I Group, participants will be randomized to the treatment HD-tDCS or sham groups using the Taves covariate adaptive randomization method³⁸. Using this method, a new participant will be sequentially assigned to a group based upon the previous assignments of other participants and certain covariates³⁹. The first eight TMD participants will be randomized by coin flip and the remaining TMD participants will be randomized by age and gender, following the Taves covariate adaptive randomization protocol.

5.4.2 *Masking Procedures*

The PI, Co-Investigator, and any members of the research staff who will be analyzing study data (with the exception of the coordinator[s]/biostatistician) will be masked to participant treatment. The research coordinator and any study staff who will be NOT involved in the treatment of the study participants in the HD-tDCS study component will be unmasked in order to promptly address any emergency directly or indirectly associated with the procedure for safety reasons. The research coordinators are not masked, and thus are able to blind the machines prior to administration of the stimuli. The biostatistician transmits the code to the coordinator in a manner that keeps the investigators and co-I's blinded. Patients will be allowed to know the type of stimulation they received, active or sham, at the end of the study if requested.

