6 STUDY INTERVENTION

6.1 Study Procedural Intervention(s) Description

We will conduct a single-center, sham-controlled, double-blinded study to prospectively investigate the neuromodulatory effects of M1 HD-tDCS in pain intensity and brain molecular neuroplasticity in a cohort of chronic TMD patients. The subjects will participate in 10 daily sessions (e.g., Monday – Friday for two weeks), either active or sham M1 HD-tDCS.

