6.2 Administration of Procedural Intervention

For the M1 HD-tDCS, four electrodes arranged at the corners of a 4 cm x 4 cm square will be centered over the motor cortex contralateral to the side with the worst TMD pain. The upper anode will be placed on C3/C4 and lower anode on C5/C6, and the upper and lower cathodes will be placed anteriorly on FC3/4 and FC5/6, respectively, using the International Electroencephalography (EEG) 10-20 system and confirmed by TMS to determine the precise scalp position⁴⁰. The vertex will be found by measuring the midpoint between nasion and inion and the midpoint between the pre-auricular areas. Then the midpoint from the vertex to the pre-auricular point on the side contralateral to the patient's worst pain will be marked so that stimulation could be applied to the same spot each day. A perforated cloth cap with a chinstrap will be placed on the patient's head to secure plastic casings of each electrode in the desired position. Approximately 3 mL of Lectron II Conductivity Gel will be injected into the electrode casings. Ag/AgCl sintered ring electrodes with the rough surface directed towards the skin will be placed into the gel and held in place with plastic caps. In the active HD-tDCS group, 2 mA current stimulation will be applied for 20 min. For sham-controlled tDCS sessions current will be applied for 30 sec only—this is a frequent method of sham stimulation⁴¹ as sensations arising from tDCS treatment occur mostly at the beginning and end of application. Nonetheless, groups will be composed of different, tDCS-naïve patients to avoid comparison between sham and active tDCS from ongoing and previous experiences.

These HD-tDCS sessions will be conducted by study staff trained in the technique by the PI. Sessions will occur at the University of Michigan. A licensed physician will be available by pager at all times.

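### Section 5.4.2 unmasks staff not involved in HD-tDCS treatment, which conflicts with section 2.1.4 and permits unmasked staff to collect outcomes

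*Combined protocol and SAP*

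**What the plan says.** The Protocol Summary describes a "single center, two-arm double-masked, randomized investigation and modulation" of mu-opioid mechanisms, and section 6.1 says "We will conduct a single-center, sham-controlled, double-blinded study".

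Section 5.4.2 sets the masking by role. The PI and the Co-Investigator are masked; for analysts the rule is that "any members of the research staff who will be analyzing study data (with the exception of the coordinator[s]/biostatistician) will be masked to participant treatment". Unmasking applies to the coordinator; beyond that role, "any study staff who will be NOT involved in the treatment of the study participants in the HD-tDCS study component will be unmasked"; the reason given is "in order to promptly address any emergency directly or indirectly associated with the procedure for safety reasons". It adds: "The research coordinators are not masked, and thus are able to blind the machines prior to administration of the stimuli". The biostatistician passes the code to the coordinator, and patients may ask for their allocation once the study has ended.

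Section 2.1.4 describes the sessions. Current and duration are "set by the investigator's unblinded designee before each treatment session". The same person watches the unit throughout the session, and its panel is kept out of sight of subjects and blinded investigators.

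Section 6.2 says "These HD-tDCS sessions will be conducted by study staff trained in the technique by the PI" but gives no masking status for them.

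Table 2 gives the timing of each outcome. It does not give the role of the person who collects it.

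**The concern.** In a sham-controlled pain trial, the staff who need to know the arm are those who hold the code and those who set the device. Staff who meet the patient when pain is recorded, or who perform an examination, should not know it. The clause in 5.4.2 does roughly the opposite: it unmasks people because they are outside the treatment sessions, and it makes no exception for those who collect outcomes.

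The sponsor's own text shows that masking deserves care here. Section 2.3.1 notes that skin redness is more common under active stimulation and could compromise it. If staff who know the arm hand out the VAS at the 4-week visit, or carry out the DC/TMD examination or algometry, the result is open to a criticism that the protocol cannot answer.

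**Working it through.** No arithmetic applies. The plan states no figure on this point, and the question is who is masked. The check sets the masking statements beside the outcome schedule.

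**Step 1. Masking by role.**

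| Role | Section 5.4.2 as written | Section 2.1.4 |
|---|---|---|
| Subject | Learns the arm only at the end of the study, on request | Cannot see the panel |
| PI, Co-Investigator | Masked | Blinded investigators cannot see the panel |
| Staff analysing data | Masked, except coordinators and biostatistician | Not addressed |
| Biostatistician | Exempt from masking; passes on the code | Not addressed |
| Coordinator | Unmasked; prepares the machines | Could be the designee; not stated |
| Non-coordinator who sets and monitors the device | Not covered by the unmasking clause | Unblinded |
| Other staff outside the sessions | Unmasked | No role that needs the arm |

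The two sections agree on subjects and investigators and can agree on the coordinator. They conflict on the last two rows. The clause also fits its own rationale poorly: emergencies arising from the procedure are given as the reason to unmask people who are not at the procedure.

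**Step 2. Does deleting the word NOT settle it?** Without that word, staff involved in treatment would be unmasked, which agrees with 2.1.4. But section 7.2 and footnote 6 of the questionnaire part of Table 2 place VAS, GeoPain, the short McGill form and PANAS before and after each session, when those same staff are present. The coordinator is unmasked on either reading. Neither reading bars an unmasked person from collecting outcomes, so the gap stays open.

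**Step 3. Which measurements are exposed?** Only those after randomization. The primary baseline is Screening (section 3.2.1), and randomization is on Day 1 of HD-tDCS (section 7.2), so nobody can know the arm at baseline. After randomization:

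- Primary VAS at Follow-up #2: scored by the patient. Section 16.3 has questionnaires captured on paper or eCRF, so staff contact is plausible.
- VAS at rest and during the pain challenge at PET #2 (secondary endpoint): patient ratings given within a staff-run session.
- GeoPain (secondary endpoint): entered on a mobile device (Table 2).
- DC/TMD examination at Follow-ups #2 and #3: performed by an examiner named on the form. It is not a listed endpoint in section 3.2.
- QST at PET/MRI #2: includes algometry. It is not a listed endpoint in section 3.2.

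**Step 4. Size.** A bias estimate would need the between-arm difference produced by staff cueing alone, and no section supplies one.

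**The case against.** The strongest reply is that this is a drafting slip in an otherwise sound scheme. The same paragraph masks the PI, the Co-Investigator and the analysts. Patients score their own pain and learn their arm only at the end. The coordinator named in 5.4.2 may be the designee of 2.1.4. Those who collect outcomes may in practice be masked investigators, and the Manual of Procedures, which section 18 keeps separate from the protocol, may say so. An HD-tDCS Sham/Placebo Assessment is also scheduled at the treatment visits.

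Most of this stands, and it limits the point. It does not remove it. The clause is an explicit rule in the governing document, it conflicts with 2.1.4, and removing one word would not say who may collect outcomes.

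Three stronger readings are tempting, and the documents do not support them:

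- A reader might infer that the trial is not double-masked. Subjects, PI and Co-Investigator remain masked under either reading of the clause.
- A reader might infer that unmasked staff will collect the pain outcomes. The documents permit this but never name the collectors.
- A reader might infer that assessor masking is lost for the primary endpoint. Its rater is the masked patient, and its baseline precedes randomization.

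**Conclusion.** The point holds as an internal contradiction with a real but bounded risk. As written, section 5.4.2 unmasks the coordinator and all staff not involved in HD-tDCS treatment, apart from the PI, the Co-Investigator and the data analysts. Section 2.1.4 identifies the device designee as the unblinded person. Together they leave unmasked staff free to collect outcomes.

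Two routes to bias remain: cueing of masked patients when they complete the VAS or other ratings, and examiner influence on the DC/TMD examination, QST and PET-session ratings. The first touches the primary endpoint only indirectly.

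The size cannot be estimated from the documents. A reader might assume some fraction of a standard deviation for cueing and convert it into a false-positive rate. Any such value would be invented and could as well be zero, and ordinary expectancy affects both arms. The conclusion assumes only that the protocol text governs and that no separate procedure overrides it. The text should be corrected, but the design does not need to change.

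**What to change.** Reconcile sections 5.4.2, 2.1.4 and 6.2:

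1. Delete the clause in 5.4.2 that unmasks staff not involved in treatment.
2. Limit unmasking to the biostatistician who holds the code and the coordinator or designee who sets the device. The biostatistician must be named, because a rule confined to the designee or coordinator would mask the person who transmits the code. The unmasked designee already monitors every session under 2.1.4, so someone who knows the arm is still at hand, which was the stated purpose of the clause.
3. State in 6.2 which session staff are masked and which are not.
4. State that whoever administers the post-randomization VAS, GeoPain, QST, DC/TMD examination or PET ratings is masked to that subject's arm.
5. Where an unmasked coordinator must be present, have the subject enter VAS and GeoPain without staff prompting, for example on the mobile device already used for GeoPain.

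The cost is a short text amendment, plus some scheduling and delegation-log work to keep the roles separate. Staffing is not described, so whether an extra person would be needed cannot be judged from the documents.

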5.5 Subject Withdrawal

5.5.1 *Reasons for Withdrawal*

Subjects are free to withdraw from participation in the study at any time upon request. An investigator may terminate a study subject's participation in the study if:

- Any clinical adverse event (AE), laboratory abnormality, or other medical condition or situation occurs such that continued participation in the study would not be in the best interest of the subject.
- The subject meets an exclusion criterion (either newly developed or not previously recognized) that precludes further study participation.

5.5.2 *Handling of Subject Withdrawals or Subject Discontinuation of Study Intervention*

Subjects wishing to withdraw from the study at any time may do so and should notify the study team. For payment to these subjects, see Section 5.3.

Withdrawals need not be replaced, but may be on a case-by-case basis, at the PI's discretion. The power calculations allow for a 20% dropout rate.

5.6 Premature Termination or Suspension of Study

This study may be suspended or prematurely terminated if there is sufficient reasonable cause. Written notification, documenting the reason for study suspension or termination, will be provided by the suspending or terminating party to the investigator, funding agency, the sponsor and regulatory authorities. If the study is prematurely terminated or suspended, the principal investigator will promptly inform the IRB and will provide the reason(s) for the termination or suspension.

Circumstances that may warrant termination include, but are not limited to:

- Determination of unexpected, significant, or unacceptable risk to subjects.
- Insufficient adherence to protocol requirements.
- Data that are not sufficiently complete and/or evaluable.
- Determination of futility.

6 STUDY INTERVENTION

6.1 Study Procedural Intervention(s) Description

We will conduct a single-center, sham-controlled, double-blinded study to prospectively investigate the neuromodulatory effects of M1 HD-tDCS in pain intensity and brain molecular neuroplasticity in a cohort of chronic TMD patients. The subjects will participate in 10 daily sessions (e.g., Monday – Friday for two weeks), either active or sham M1 HD-tDCS.

6.2 Administration of Procedural Intervention

For the M1 HD-tDCS, four electrodes arranged at the corners of a 4 cm x 4 cm square will be centered over the motor cortex contralateral to the side with the worst TMD pain. The upper anode will be placed on C3/C4 and lower anode on C5/C6, and the upper and lower cathodes will be placed anteriorly on FC3/4 and FC5/6, respectively, using the International Electroencephalography (EEG) 10-20 system and confirmed by TMS to determine the precise scalp position⁴⁰. The vertex will be found by measuring the midpoint between nasion and inion and the midpoint between the pre-auricular areas. Then the midpoint from the vertex to the pre-auricular point on the side contralateral to the patient's worst pain will be marked so that stimulation could be applied to the same spot each day. A perforated cloth cap with a chinstrap will be placed on the patient's head to secure plastic casings of each electrode in the desired position. Approximately 3 mL of Lectron II Conductivity Gel will be injected into the electrode casings. Ag/AgCl sintered ring electrodes with the rough surface directed towards the skin will be placed into the gel and held in place with plastic caps. In the active HD-tDCS group, 2 mA current stimulation will be applied for 20 min. For sham-controlled tDCS sessions current will be applied for 30 sec only—this is a frequent method of sham stimulation⁴¹ as sensations arising from tDCS treatment occur mostly at the beginning and end of application. Nonetheless, groups will be composed of different, tDCS-naïve patients to avoid comparison between sham and active tDCS from ongoing and previous experiences.

These HD-tDCS sessions will be conducted by study staff trained in the technique by the PI. Sessions will occur at the University of Michigan. A licensed physician will be available by pager at all times.

6.3 Procedures for Training of Clinicians on Procedural Intervention

All study clinicians will be trained in HD-tDCS technique by the PI (or trained designee) according to the study Manual of Procedures.

6.4 Assessment of Clinician and/or Subject Compliance with Study Procedural Intervention

Study staff performing each procedural administration will be trained in a standardized manner so as to assure compliance with the protocol. Likewise, the team will reassess clinician and subject compliance with study procedures and instructions at a study level during weekly meetings to assure quality control.

7 STUDY SCHEDULE

See Table 2. Schedule of Events. Adverse events will be recorded from the time that the subject signs the informed consent until the subjects leaves the study. Any AE reported voluntarily by the patients after the study, potentially associated with the procedures, will be documented and shared with the IRB.

7.1 Healthy Volunteers

Prescreening (Study Week -8)

Subjects interested in the study will be prescreened via a phone interview using an IRB-approved checklist.

Screening (Study Week -3)

The activities assigned to the Screening Visit will be completed within ~21 days prior to the second of two scans (see Baseline PET/MRI). Following the informed consent process, subjects will undergo a baseline assessment comprised of a medical/dental history with limited physical, listing of medication history (6 months) and review of eligibility. They will then complete questionnaires, as listed in the study schedule (Table 2).

Baseline PET/MRI (Study Week -1)

Within 7 days of each other, subjects will undergo an MRI, as well as a PET scan that uses an [¹¹C]carfentanil radioligand, with a masseter muscle pain challenge via a 5% hypertonic saline intramuscular infusion. Pain questionnaires will also be completed during this visit window. Completion of all procedures may require more than one clinic visit and an additional week window will be allowed to account for scheduling issues.

At this point, all Healthy Volunteer subjects will have completed participation in the study.

7.2 TMD Patients

Prescreening (Study Week -8)

Chronic TMD subjects interested in the study will be prescreened via a phone interview using an IRB-approved checklist.

Screening
(*Study Week -3*)

The activities assigned to the Screening Visit will be completed within 3 weeks prior to the first session of Week 1. Following the informed consent process, subjects will undergo a baseline assessment and the completion of questionnaires, as listed in the study schedule (Table 2). The baseline visit will include a medical/dental history with limited physical that involves clinician assessed DC/TMD (Diagnostic Criteria/Temporomandibular Disorder) status. Also covered are a comprehensive medication history (6 months) and a review of eligibility.

Baseline PET/MRI
(*Study Week -1*)

Within 7 days preceding randomization and the first study treatment, subjects will undergo an MRI, as well as a PET scan that uses an [¹¹C]carfentanil radioligand, with a masseter muscle pain challenge via a 5% hypertonic saline intramuscular infusion. Pain questionnaires will also be completed during this visit window. All procedures are targeted for the week prior to HD-tDCS; however, due to occasional scheduling difficulties, they may be completed within 14 days prior to Day 1 of HD-tDCS. Completion of all procedures may require more than one clinic visit.

Treatment HD-tDCS
(*Study Weeks 1 through 2*)

Beginning at Day 1 of HD-tDCS, subjects will be randomized to active treatment or sham procedure. They will then attend 10 sessions, 1 each weekday (Monday through Friday) over a 2-week period, and will receive either the M1 HD-tDCS treatment or the sham treatment, preceded and followed by questionnaires. Missed days can be doubled and/or rescheduled within the 2-week schedule, as necessary, with study team approval.

Follow-up PET
Follow-up MRI &
First Follow-up Visit
(*Study Week 3*)

Within 7 days following the last study treatment, subjects will undergo an MRI as well as a PET scan that uses an [¹¹C]carfentanil radioligand with a masseter muscle pain challenge via a 5% hypertonic saline intramuscular infusion. Pain questionnaires will also be completed during this visit window. All procedures are targeted for the week following completion of HD-tDCS; however, due to occasional scheduling difficulties, they may be completed within 14 days following Day 10 of HD-tDCS. Completion of all procedures may require more than one clinic visit.

Follow-Up #2 & #3
(Study Weeks 6 and 10)

Pain questionnaires will be completed again at 4 weeks (Follow-Up #2) and 8 weeks (Follow-Up #3) after the final treatment day (Study Weeks 6 and 10, respectively).

Table 2

SCHEDULE OF EVENTS – I. Procedures

Procedures	Phone PreScreening	Screening	PET/MRI #1 (Baseline) ^{1,2}	HD-tDCS #1-10 ⁸	PET/MRI #2/ Follow-up #1 ^{1,2}	Follow-up #2	Follow-up #3	Early Termination ³
Visit	P	1	2	3A-J	4	5	6	ET
Study Week	-8	-3	-1	1 – 2	3	6 (1 mth)	10 (2 mths)	N/A
Prescreening Script/Checklist	X ⁵							
Informed Consent		X ⁵						
Adverse Events		X ⁵	X ⁵	X	X	X	X	X
Medical/Dental History and Physical		X ⁵						
Medication History/ Concomitant Medications		X ⁵	X ⁵	X	X	X	X	
Quantitative Sensory Testing (QST)			X ⁵		X			
Eligibility Assessment ⁴		X ⁵						
PET Scan 
 Pregnancy Test (Dip)⁷ Drug Screen⁷ Blood sample for biomarkers Masseteric Pain Challenge (5% hypertonic saline) 			X ⁵		X			
Blood sample for genetic testing			X ⁵					
MRI Scan			X ⁵		X			
RANDOMIZATION				Week 1				
HD-tDCS (M-F for 2 weeks)				X ⁶				

¹ Target dates for PET/MRI are the week prior to Day 1 HD-tDCS session (Baseline) and the week after completion of HD-tDCS sessions (Follow-up); an additional week window is allowed to account for scheduling issues.

² Procedures may require more than one clinic visit.

³ Applicable if subject completes an in-person visit.

⁴ If subject is deemed eligible, schedule subject visits and provide subject with instructions for PET & MRI.

⁵ Healthy Volunteer subjects complete only these procedures indicated.

⁶ Missed days can be doubled in the (M-F) x 2 schedule, with study team approval. See Section 7.

⁷ Completed within 24 hours prior to PET session

⁸ HD-tDCS sessions will be scheduled M-F. See Section 7.2.

Table 2
SCHEDULE OF EVENTS – II. Questionnaires

Questionnaires	Phone PreScreening	Screening	PET/MRI #1 (Baseline) ^{1,2}	HD-tDCS #1-10 ⁸	PET/MRI #2/ Follow Up#1 ^{1,2}	Follow Up #2	Follow Up #3	Early Termination ³
Visit	P	1	2	3A-J	4	5	6	ET
Study Week	-8	-3	-1	1 – 2	3	6 (1 mth)	10 (2 mths)	N/A
Demographics		X ⁷						
Beck Depression Inventory		X ⁷						
DC/TMD Examination Form		X ⁷				X	X	
Expectation of Effect VAS		X						
McGill Pain Questionnaire (MPQ) (Long Form)		X						
MPQ (Short Form) ⁶		X	X	X	X	X	X	
Positive and Negative Affect Schedule (PANAS) ⁶		X ⁷	X ⁷	X	X	X	X	
GeoPain (via mobile device) ⁶		X	X	X	X	X	X	
Visual Analog Scale (VAS) ⁶		X	X	X	X	X	X	
Graded Chronic Pain Scale		X			X	X	X	
Brief Pain Inventory (BPI; Short)		X			X	X	X	
Pittsburgh Sleep Quality Index		X ⁷			X	X	X	
PET Subject Information Sheet			X ⁷		X			
tDCS Effects Questionnaire				X	X	X	X	
HD-tDCS Sham/Placebo Assessment				X				
DC for TMD Symptom Questionnaire		X ⁷			X	X	X	

¹ Target dates for PET/MRI are during the week prior to Day 1 HD-tDCS session (Baseline) and during the week after completion of HD-tDCS sessions (Follow-up); an additional week window is allowed to account for scheduling issues. The "Magnetic Resonance (MR) Safety Screening Form" is completed prior to each MRI scan. See Section 2.3.4.

² Procedures may require more than one clinic visit.

³ Applicable if subject completes an in-person visit.

⁴ If subject is deemed eligible, schedule subject visits and provide subject with instructions for PET & MRI.

⁵ Missed days can be doubled in the (M-F) x 2 schedule, with study team approval. See Section 7.

⁶ These assessments will be conducted at Screening, before and after MRI/PET and tDCS Sessions, and at Follow-up visits.

⁷ Questionnaires to be completed by healthy volunteer subjects at the timepoints indicated.

⁸ HD-tDS sessions will be scheduled M-F. See Section 7.2.

